A Self-directed Positive Psychology Intervention for Individuals with Newly Diagnosed Multiple Sclerosis

NTC06891937

10.15.21

Institutional Review Board Intervention/Interaction Detailed Protocol

Principal Investigator: [name]

Project Title: A Self-directed Positive Psychology Intervention for Individuals with
Newly Diagnosed Multiple Sclerosis

Version Date: 10.15.21

1. Background and Significance

Multiple sclerosis (MS) is a chronic autoimmune disease of the central nervous system that affects both physical and mental health. Mental health comorbidities including depression and anxiety are common [1-2] and health-related quality of life (HRQOL) is often reduced [3-4]. Several key elements of successful adaptation to MS have been identified including maintenance of emotional balance, preservation of healthy relationships, absence of psychological disorders, low levels of negative affect and high levels of positive affect [5].

Positive psychology (PP) uses systematic exercises such as writing a letter of gratitude or remembering a past success to increase the frequency and intensity of specific positive psychological constructs such as positive affect and optimism [6-7]. We have previously demonstrated the feasibility and acceptability of a five-week, at-home, trainer-guided PP intervention for individuals with MS [8]. The intervention was associated with significantly greater increases in positive affect, optimism, general health and resilience and decreases in anxiety in the intervention group compared to the controls. Despite the benefits of the trainer-guided PP trial, the program has several limitations. First, it requires funding for a dedicated study trainer limiting its scalability. Second, the improvements seen following the completion of the PP exercises may have been related to engagement with the study trainer and not the PP program itself. Third, the individuals who participated in the trial had a mean disease duration of more than 20 years and it is not clear if the observed findings apply across the disease course.

We would like to evaluate the feasibility, acceptability and efficacy of a self-guided version of the PP intervention in individuals with recently diagnosed with MS. An MS diagnosis creates a crisis for the individual and his/her family. Typical initial emotional responses include fear, denial, anger and resentment [9]. The introduction of techniques to increase positive emotional experiences early on in the disease course might promote successful adaptation to living with MS. If we are able to demonstrate the feasibility, acceptability and efficacy of a self-

directed PP program, it could be made available to all newly diagnosed patients seen at the Brigham Multiple Sclerosis Center.

2. Specific Aims and Objectives

Specific Aim 1: Evaluate the feasibility and acceptability of a five-week self-directed PP training intervention for newly diagnosed patients with MS. We will assess the feasibility of the intervention by calculating the proportion of subjects who complete four of the five weekly exercises. We will determine the acceptability of each exercise by having subjects rate the ease and utility of each exercise after it is completed.

[figure not shown]
Specific Aim 2: Examine the efficacy of PP training to improve positive affect, emotional function and HRQOL. We will compare positive affect in subjects in the intervention and control group at the completion of the intervention phase. We will also assess between-group differences in depression, anxiety, fatigue, resilience and HRQOL following the intervention phase.

Specific Aim 3: Determine if improvements in positive affect, emotional function and HRQOL following PP training are maintained. For subjects in the intervention group who demonstrate a benefit from PP intervention, we will determine if that benefit is maintained by comparing positive affect, depression, anxiety, fatigue, resilience and HRQOL at the completion of the intervention and extension phases.

3. General Description of Study Design

This is a phase I randomized controlled trial (RCT) to examine the feasibility, acceptability and efficacy of a self-directed PP training intervention to increase positive affect in newly diagnosed patients with MS. The RCT will include a five-week intervention phase and a five-week extension phase.

Schema:

4. Subject Selection

Thirty subjects with newly diagnosed MS will be enrolled at the Brigham MS Center.

Inclusion criteria:

1. Diagnosis of MS according to the McDonald 2017 diagnostic criteria with onset of symptoms within the last 2 years
2. Age 18-65
3. Ability to speak, read and write in English

Exclusion criteria:

1. Moderate or marked cognitive abnormalities identified by the treating neurologist during routine clinical visits to the Brigham MS Center that would preclude meaningful participation in the PP exercises.

All newly diagnosed MS patients seen at the Brigham MS Center will be eligible to participate. Patients will be approached by their physicians at the time of their routine clinical visits to the center. Interested individuals will meet with a member of the research staff to learn about the study in more detail. Flyers will also be posted at the Brigham MS Center.

5. Subject Enrollment

Individuals with MS will be given a copy of the consent document to review. They will have the opportunity to discuss the study with their physician as well as other members of the research study staff prior to giving consent. Individuals may choose to enroll at the time of their clinical visit, or they may enroll at a later date. Consent will be obtained by study investigators or research coordinators listed on the protocol.

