6. STUDY PROCEDURES

Enrollment Visit (60 minutes)

Subjects will be enrolled at the Brigham MS Center at the Brigham and Women's Hospital. At enrollment, subjects will be consented and assigned a study subject ID. Subjects will complete a battery of PRO measures in REDCap, a secure web application for building and managing online surveys. The PRO measures include:

1. Positive and Negative Affect Scale (PANAS) [11] is comprised of two 10-item mood scales, one measuring positive affect and the other negative affect.
2. Life Orientation Test-Revised (LOT-R) [12] is a 6-item measure of optimism and pessimism and the most widely used measure of optimism.

3. NeuroQoL [13] is a set of self-report measures developed through a collaborative, multisite NINDS-sponsored research initiative to construct psychometrically-sound and clinically-relevant HRQOL tools for individuals with neurological conditions such as stroke, MS and Parkinson's disease. It covers 12 domains including Ability to Participate in Social Roles and Activities, Anxiety, Cognitive Function, Depression, Emotional and Behavioral Dyscontrol, Fatigue, Lower Extremity Function, Positive Affect and Well-Being, Satisfaction with Social Roles and Activities, Sleep, Stigma and Upper Extremity Function.
4. Brief Resilience Scale (BRS) [14] is a 6-item scale that measures the ability to bounce back or recover from stress.

After enrollment, a computerized random number generator will be used to randomize subjects to the intervention or control group.

Intervention Phase (5 weeks)

In the intervention phase (Phase I: Weeks 1-5), subjects randomized to the intervention group will be given the study participant manual and asked to set up a time for weekly phone calls with the study coordinator. They will complete five weeks of PP exercises, one exercise per week. They will be asked to rate their mood prior to and after completing each exercise. They will also be asked to rate the ease and utility of each exercise. The weekly calls with the study coordinator will be used to document and discuss the ease and utility scores recorded by subjects at the completion of the weekly exercise. The control group will have no study activities during the intervention phase and will be considered a wait-list control. At the completion of the intervention phase, all subjects will be emailed a link to complete PRO measures in REDCap.

Extension Phase (5 weeks)

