In the extension phase (Phase II: Weeks 6-10), subjects in the control group will receive their study participant manual in the mail. They will be contacted by the study coordinator to set up weekly phone calls. They will complete the PP intervention as described above. The intervention group will complete no study activities in the extension phase. At the completion of the extension phase, all subjects will be emailed a link to complete PRO measures.

Intervention: The PP intervention consists of five weeks of self-directed PP training using the following exercises:

1. Gratitude for positive events: Recall three positive events that occurred in the past week and write about the events and how the events made you feel.
2. Personal strengths: Complete a brief survey of personal strengths and select a strength such as perseverance or humility and use it deliberately in the next 24 hours. Write about how you used the strength and how you felt while using it.

3. Gratitude letter: Recall another individual's kind act that resulted in joy, relief, serenity or other positive feelings. Write a letter to the person describing feelings of gratitude associated with this event.
4. Enjoyable and meaningful activities: Intentionally complete three acts in a single day – a pleasurable act done alone, a pleasurable act done with others and a meaningful or important act.
5. Remembering past successes: Focus on a time when you experienced success and write about the event and the positive feelings and thoughts you had during the event

These exercises have all been described by Huffman et al. [10, 15]. Exercises may require anywhere from 15 minutes to several hours to complete.

7. Risks and Discomforts

There are no major risks associated with participating in the study. Subjects may experience discomfort writing about emotional aspects of their lives. If they do experience discomfort, they may choose not to complete the weekly PP assignments. If they feel their participation is becoming too burdensome or is exacerbating ongoing symptoms, they have the option to decline further participation and withdraw from the study. They may also be referred to a mental health provider at the Brigham MS Center.

8. Benefits

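### Acceptability is scored only from completed exercises, and no reason for non-completion is described, so the scores may be too favourable; the existing weekly calls could close the gap cheaply

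*Combined protocol and SAP*

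**What the plan says.** Specific Aim 1 (Section 2) has two parts. Feasibility is assessed by "calculating the proportion of subjects who complete four of the five weekly exercises". Acceptability is determined by "having subjects rate the ease and utility of each exercise after it is completed".

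Section 6 (Intervention Phase) follows the aim: the coordinator's weekly calls are used to "document and discuss the ease and utility scores recorded by subjects at the completion of the weekly exercise". One sentence in the same paragraph asks for the ratings without mentioning completion, but the next sentence and the aim itself tie them to finished exercises. The wait-list group follows the same procedure in the extension phase: "They will complete the PP intervention as described above".

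The protocol also anticipates that some exercises will not be finished. On time, Section 6 says: "Exercises may require anywhere from 15 minutes to several hours to complete". On discomfort, Section 7 says: "If they do experience discomfort, they may choose not to complete the weekly PP assignments". For subjects who find participation "too burdensome or is exacerbating ongoing symptoms, they have the option to decline further participation and withdraw from the study", leaving is expressly allowed.

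On use of the results, Section 1 says that if the program is shown to be feasible, acceptable and efficacious, "it could be made available to all newly diagnosed patients seen at the Brigham Multiple Sclerosis Center". Section 8 makes a similar conditional statement. Section 10 has the team review subject satisfaction every week but names no record for each exercise.

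**The concern.** The measurement rule selects on something close to what is being measured. A subject who stops an exercise because it is upsetting, too long or unappealing has found it less acceptable, yet under the plan as written contributes no ease or utility score for it. Those who remain to rate it are the ones who got through it.

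The aim is framed exercise by exercise, so the effect could fall unevenly. An exercise that many subjects abandon could still show good scores from the few who finished it.

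Acceptability is half of Aim 1 and one of the three conditions attached to offering the program more widely. Reasons that are not asked for at the time are hard to recover later. Without them, a report cannot separate skips caused by the exercise from skips caused by illness or a busy week.

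**Working it through.** **Plan's own figure.** The protocol gives no rating scale, expected score or skip rate, so there is no acceptability figure to reproduce. The sample-size statement in Section 9 concerns the feasibility proportion and does not bear on this point.

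**What is described for each assigned exercise** (Sections 2, 6 and 7 read together):

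| Status of the exercise | Counts towards 4 of 5 | Ease and utility score described | Reason described |
|---|---|---|---|
| Completed | Yes | Yes | Not needed |
| Started, not finished | No | No | No |
| Skipped | No | No | No |
| Due after withdrawal | No | No | No |

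Only the first row yields a score.

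**Does the 4-of-5 measure fill the gap?** Inputs: 30 subjects (Section 4) and five exercises (Section 6). Assumptions: both groups contribute, and 4 of 5 means at least four.

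- Assigned exercises: 30 × 5 = 150.
- A subject who meets the measure misses 0 or 1; a subject who does not misses 2 to 5.
- If k subjects meet it, the number unrated lies between 2(30 − k) and k + 5(30 − k) = 150 − 4k.
- At the best possible result, k = 30, the range is 0 to 150 − 120 = 30, and 30/150 = 20%.
- Those 30 could be spread evenly, 30/5 = 6 per exercise, leaving 30 − 6 = 24 raters for each. They could also all fall on one exercise, leaving it with no raters while the other four have 30 each.

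If only an intervention group of 15 contributed (equal allocation is assumed; the protocol does not state it), 15 of 15 meeting the measure still allows 0 to 15 of 15 × 5 = 75, again up to 20%. These are limits implied by the 4-of-5 definition, not predictions of how much skipping will occur.

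**Size of any overstatement.** Take the subjects who started a given exercise. Let m be the share who did not finish, a the mean score of finishers, and b the mean score the non-finishers would have given. The mean over all starters is (1 − m)a + mb, so the finishers' mean is too high by

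a − [(1 − m)a + mb] = m(a − b).

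For example, with an assumed m = 0.20 the overstatement is one fifth of the gap a − b. If a = b, it is zero. The protocol supplies neither m nor a − b, so no value can be given. The formula does not cover subjects who never tried the exercise, because they have no experience of it to rate. For them the missing information is the reason, not a score.

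**The case against.** The strongest defence is that ratings from people who did an exercise are a legitimate definition of its acceptability, and that non-completion is already counted under feasibility. The two are reported together, and widespread skipping would lower the feasibility result. Much of this stands. Scores from raters should remain the main result, and a never-tried exercise should not be treated as having a hidden low score. What does not stand is that feasibility supplies the missing information. It is one yes/no per subject, with no exercise and no reason.

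A second defence is that the information may exist anyway. Rater counts per exercise can be derived from the planned data. The mood ratings before and after each exercise might reveal some unfinished attempts, and coordinators may hear reasons on the calls. This also stands in part. A reader might infer that reasons are not collected at all; the protocol does not support that. It only fails to describe their collection, and neither the call forms nor the participant manual is shown. Even so, a count shows which exercise was missed, not why, and an informal remark cannot be analysed.

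A third defence is that this is a 30-subject pilot with no acceptability threshold, so no stated decision could change. That is correct, and it limits the severity. It does not remove the point, since learning why exercises are not done is a main use of such a pilot.

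**Conclusion.** The point holds as a low-severity, inexpensive improvement. Followed as written, the plan yields acceptability scores from finishers, while its own text names discomfort and burden as grounds for not finishing. The scores may be too favourable to the extent that non-completion reflects low acceptability. The amount cannot be computed and is zero if the two are unrelated. The only firm figure is that full success on 4 of 5 is compatible with up to 30 of 150 assigned exercises being unrated, given the assumptions stated above.

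A reader might go further and infer that the acceptability result will be wrong, or that the decision to offer the program would be reversed. The protocol supports neither. It gives no skip rate, no rating gap and no cut-off, and its statements about wider use are conditional. Section 9 contains no acceptability analysis; that is a matter of detail on which this point does not rest.

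**What to change.** On the existing weekly calls, record for each assigned exercise:

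- whether it was completed, attempted but not finished, or not done;
- if not completed, the main reason: discomfort, burden, dislike, unrelated, or not known;
- ease and utility for any attempt, not only for finished exercises.

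At withdrawal, ask for the reason if the subject is willing. Subjects' freedom to skip or withdraw is unchanged.

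In the report, keep the raters' scores as the main acceptability result. Beside them, give the numbers assigned, completed and rated for each exercise, listing separately those that fell due after a withdrawal. Add one sensitivity analysis that counts non-completion for discomfort, burden or dislike as not acceptable, for example by assigning the lowest score on whatever scale is used.

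The cost is a few items on at most 30 × 5 = 150 calls already planned, one voluntary question at withdrawal, and short additions to Sections 2, 6 and 9. If the call forms already capture this, only the text needs adding. Sample size and intervention do not change. The downsides are slightly longer calls, a possibly less favourable acceptability figure, and reasons still missing for subjects lost without contact. Exercises never tried stay unrated, so the change shows why scores are absent rather than supplying them.

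### Should a trial in newly diagnosed MS time eligibility from diagnosis rather than from symptom onset?

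*Combined protocol and SAP*

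**What the plan says.** Section 4 (Subject Selection) opens with "Thirty subjects with newly diagnosed MS will be enrolled at the Brigham MS Center". Inclusion criterion 1 is then "Diagnosis of MS according to the McDonald 2017 diagnostic criteria with onset of symptoms within the last 2 years". The other criteria cover age, English and cognitive status. No limit on time since diagnosis is written anywhere, and newly diagnosed is not defined separately.

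After the numbered criteria, the paragraph on how patients are approached begins "All newly diagnosed MS patients seen at the Brigham MS Center will be eligible to participate".

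Elsewhere the population is also named by diagnosis. Aim 1 in Section 2 is to "Evaluate the feasibility and acceptability of a five-week self-directed PP training intervention for newly diagnosed patients with MS". Section 1 gives two strands of rationale. One is the event of diagnosis: "An MS diagnosis creates a crisis for the individual and his/her family". The other is early disease: "The introduction of techniques to increase positive emotional experiences early on in the disease course might promote successful adaptation to living with MS". Section 1 also lists, as a limitation of the earlier trainer-guided trial, a mean disease duration of more than 20 years, which left open whether its findings hold at other stages of the disease. On later use, Section 1 says that if the programme succeeds "it could be made available to all newly diagnosed patients seen at the Brigham Multiple Sclerosis Center".

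**The concern.** The population is named by one event (diagnosis) and selected by another (first symptoms). Someone diagnosed last month whose symptoms began three years ago belongs to the group in the title and is covered by the recruitment sentence, yet fails criterion 1. Physicians make the first approach, so they could be working from two rules that disagree about the same patient.

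If patients with a slow route to diagnosis react differently to it, feasibility, acceptability and efficacy would go untested in part of the group who might later be offered the programme. A statement about all newly diagnosed patients would then reach beyond the sample.

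**Working it through.** **1. The plan's own figure.** Section 9 gives the only computed design figure: 80% power with N = 30, null proportion 0.5 and true proportion 0.75, by a one-sample binomial test. Alpha and sidedness are not stated; I assume two-sided 0.05.

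- Exact test: reject if X ≥ 21 of 30. Under p = 0.5, P(X ≥ 21) = 0.0214, and 20 would be too low a cut-off for 0.025. Under p = 0.75, P(X ≥ 21) = 0.803.
- Score approximation: power 0.816, required N = 28.9, so 29.

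The stated 80% is reproduced. It depends on N and the two proportions, and the date that starts the eligibility clock does not enter.

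**2. What criterion 1 implies about time since diagnosis.** Let O, D and E be the dates of symptom onset, diagnosis and enrolment. Criterion 1 requires a diagnosis at entry (D ≤ E) and E − O ≤ 2 years. Assume diagnosis does not precede symptoms (O ≤ D). Then

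E − D ≤ E − O ≤ 2 years.

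So criterion 1 caps time since diagnosis at 2 years without saying so.

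**3. Who is treated differently by the two clocks.** Compare criterion 1 with a rule of diagnosis within 2 years and no onset limit:

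| Patient | Criterion 1 | Diagnosis clock |
|---|---|---|
| Diagnosed last month, onset 3 years ago | out | in |
| Diagnosed 23 months ago, onset shortly before and within 2 years | in | in |
| Diagnosed more than 2 years ago | out | out |
| Diagnosed last month, onset 20 years ago | out | in |

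The rules differ only for recent diagnosis with onset more than 2 years ago. The 23-month patient is admitted by both, so that case shows no fault in the onset clock. The last row shows the price of the alternative: with no onset limit, disease duration is unbounded.

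**4. The recruitment sentence.** Taken literally, the sentence quoted from the approach paragraph would also override the age, language and cognitive criteria printed just above it. Nobody would apply it that way. It follows the numbered criteria and introduces how patients are approached, so the ordinary reading is that it covers newly diagnosed patients who meet those criteria.

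**5. Size.** Let s be the share of newly diagnosed patients with onset more than 2 years ago. The number needed to find 30 who pass the onset limit is 30/(1 − s). The documents give no value for s. Over an assumed range of 10% to 40%:

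- s = 0.10: 30/0.90 = 33.3, so 34 patients (33 × 0.90 = 29.7 falls short)
- s = 0.40: 30/0.60 = 50 patients

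These figures ignore refusals and the other criteria and are only as good as the assumed range.

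**The case for a change.** The strongest opposing case is that the title, Aim 1, the general design, the opening of Section 4 and the hoped-for use all name diagnosis, and only criterion 1 names onset. The mechanism given first in Section 1 is the shock of being diagnosed, and a patient with a three-year route to diagnosis meets that shock just as recently. The protocol never says that criterion 1 defines newly diagnosed. The amendment would take one line and enlarge the recruitment pool.

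Part of this stands. The term is undefined, the wording is inconsistent, and one identifiable group is excluded.

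It does not show that the onset clock is the wrong choice. The second strand of the rationale concerns early disease, and the earlier trial's limitation is expressed as disease duration; an onset limit answers both directly. Replacing it would swap one restriction for another, which is a trade-off for the investigator. Restating the population in the title and aims would alter neither who is enrolled nor any analysis. That patients with a slow diagnosis respond differently is plausible, but the documents offer no evidence of it.

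**Conclusion.** No change is needed. Criterion 1 is a usable working definition of newly diagnosed. It excludes patients with a long route to diagnosis and, provided diagnosis does not precede symptoms, admits nobody diagnosed more than 2 years ago. Choosing onset over diagnosis is a fair trade-off that the plan's own rationale supports, and the recruitment sentence is loose wording that anyone screening against the numbered criteria will read correctly.

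The criterion applies to both groups before randomization, so it cannot bias the comparison, and the 80% power (0.803 by the exact two-sided test at an assumed 0.05) is unaffected. What remains is a limit on generalization whose size cannot be derived from the documents: 34 to 50 newly diagnosed patients to find 30 is pure assumption at an excluded share of 10% to 40%. For a single-center pilot of 30 whose wider use is stated conditionally, ordinary reporting of the eligibility criterion tells readers who was studied.
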